5.8 Subject Death

5.8.1 Procedure for recording and reporting Subject Death

The investigator will document and report all subject deaths to the sponsor immediately but no later than 72 hours after becoming aware of the event.

Should death occur, the investigator should record the information in the hospital records and immediately document the information on the Death Form. By completing the form the sponsor will be notified.

Note: Refer to Table 1 'Data Collection' and Appendix G 'Data Collection Method' In case of EDC failure, notify Sponsor via Fax ([contact]) or via [contact].

Subject Death can be an outcome of a serious adverse event (SAE). Death can therefore be related to an SAE and all efforts to obtain the SAE details should be made and the Adverse Event form must be completed. Any supporting documentation (autopsy records, death certificates, hospitalization records) must be sent to SJM with the corresponding SAE and Death CRFs.

The subject's death is an Early Conclusion of the subject's participation in the investigation. Therefore, the investigator is requested to complete the Termination form.

The investigator must notify the EC, if appropriate, in accordance with national and local laws and regulations.

5.9 Document and data control

5.9.1 Traceability of documents and data

The investigator shall ensure accuracy, completeness, legibility and timeliness of the data reported to the sponsor on the electronic case report forms (eCRFs) and in all required reports. When copies of the original source document as well as print outs of original electronic source documents are retained, these shall be signed and dated by a member of the investigational site team with a statement that it is a true reproduction of the original source document.

5.9.2 Recording data

Source documents shall be created and maintained by the investigational site team throughout the clinical investigation.

The data reported on the eCRFs shall be derived from, and be consistent with, source documents, and any discrepancies shall be explained in writing.

The eCRFs shall be validated by the Principal Investigator or a delegated investigator. Any change or correction to data reported shall be dated and explained if necessary. The original entry will remain available by audit trail.

5.9.3 Review of data

The clinical investigation will be monitored by reviewing the eCRF approved by the investigators.

The following activities will occur:

- All eCRFs will be reviewed for completeness and accuracy after being uploaded into the database.
- The investigator (co-investigator) and/or delegate is notified regarding any missing or unclear/inconsistent data.

5.10 Monitoring

On site-monitoring shall be performed during the clinical investigation in order to guarantee adherence to all applicable regulations, the Clinical Investigation Plan and the signed Clinical Study Agreement. By monitoring, the Sponsor can also verify the accuracy of data collected on the accompanying eCRFs throughout the duration of the clinical investigation.

Monitoring is necessary to ensure adequate protection of the rights and safety of human subjects involved in the clinical investigation and the quality and integrity of the data obtained during the investigation. The sponsor will at the same time assess the investigational site and study team on staffing and facilities to ensure the investigation can continue in a safe and effective fashion.

During the monitoring visits, data reported on the eCRF shall be reviewed as specified in the monitoring plan.

5.10.1 Designated Monitors

Only monitors qualified by education, training and experience, which have been trained on the Clinical Investigation Plan, eCRF content, Monitoring Plan, relevant requirements and informed consent process will be allowed to perform monitoring activities during this clinical investigation. The monitor's qualifications and training will be documented by the sponsor. A list of monitors is available upon request.

5.10.2 Monitoring Plan

Prior to the start of the site monitoring activities for this clinical investigation, a project specific Monitoring Plan (MP) will be created.

At a minimum, the Monitoring Plan will include the following:

- Required activities
- Frequency of monitoring visits
- Visit Requirements
- Procedures for securing site compliance
- Monitoring report content and timelines
- Close-out procedures

The Monitoring Plan may be updated as appropriate. All revisions will be tracked.

5.11 Competent Authority (CA) Inspections

The investigator and/or delegate should contact SJM immediately upon notification of a CA inspection at the site. A clinical monitor will assist the investigator and/or delegate in preparing for the inspection.

An investigator who has authority to grant access shall permit authorized CA employees, at reasonable times and in reasonable manner, to enter and inspect any establishment where devices are held (including any establishment where devices are used or where records or results are kept).

An investigator, or any person acting on behalf of such a person with respect to the investigation, shall permit authorized CA employees, at reasonable times and in reasonable manner, to inspect and copy all records relating to the investigation.

An investigator shall permit authorized CA employees to inspect and copy records that identify subjects, upon notice that CA has reason to suspect that adequate informed consent was not obtained, or that reports required to be submitted by the investigator, to the Sponsor or EC have not been submitted or are incomplete, inaccurate, false or misleading.

5.12 Investigation Termination

The Sponsor reserves the right to suspend or terminate the investigation in an individual site or the entire clinical investigation for significant and documented reasons, at any stage, with appropriate written notice to the investigator.

The investigation will be terminated according to applicable regulations.

The investigator shall return all documents to the sponsor and notify the Ethics Committee and the Competent Authority (if applicable). Follow-up for all enrolled subjects will be as per standard of care.

5.12.1 Resuming the Clinical Investigation after Suspension

The sponsor shall conclude an analysis of the reason(s) for the suspension, implement the necessary corrective actions, and decide to lift the temporary suspension. The sponsor shall inform the Principal Investigators, EC/Head of Medical Institution or regulatory authority, where appropriate, and the regulatory authority of the rationale, providing them with the relevant data supporting this decision.

Concurrence shall be obtained from the, EC/Head of Medical Institution or regulatory authority where appropriate, before the clinical investigation resumes.

If subjects have been informed of the suspension, the Principal Investigator or authorized designee shall inform them of the reasons for resumption.

5.12.2 Investigation Conclusion

The investigation will be concluded when:

- A Close Out visit has been performed at each participating center AND
- The Final report has been provided by the sponsor

6 Risks and Benefits of the Clinical Investigation

Anticipated Adverse Events and Adverse Device Effects

Possible adverse events associated with the cardiac ablation procedure include, but are not limited to:

Cardiac Events:

- Abnormal ECG
- Angina (chest pain)
- Arrhythmia
- AV fistula
- Complete heart block
- Coronary artery injury
- Cardiac Perforation
- Cardiac Thromboembolism
- Myocardial infarction
- Obstruction/perforation/damage of the vascular system

- Death
- Dislodgement of implantable cardioverter defibrillator permanent pacing lead
- Endocarditis
- Exacerbation of pre-existing atrial fibrillation
- Heart Failure
- Hypotension heart block)
- Left atrial / esophageal fistula
- Pulmonary vein dissection
- Pulmonary vein stenosis

SJM CONFIDENTIAL AND PROPRIETARY

- Palpitation
- Pericardial effusion/cardiac tamponade
- Pericardial effusion without tamponade
- Pericarditis
- CHF exacerbation fluid overload
- Component damage to ICD or implantable pacemaker

- Pulmonary vein thrombus
- Temporary or complete heart block
- Unintended (in)complete AV, sinus node, heart block/damage
- Vessel wall/valvular damage or insufficiency
- Ventricular arrhythmia requiring defibrillation
- Bradycardia

Non-Cardiac Events:

- Air embolism
- Anesthesia reaction
- Cerebrovascular accident
- High creatinine phosphokinase (CPK)
- Infections
- Local hematomas / ecchymosis
- Laceration
- Phrenic nerve damage
- Pneumonia

- Pulmonary edema
- Pulmonary embolism
- Pulmonary hypertension
- Pleural effusion
- Pseudoaneurysm
- Respiratory depression
- Skin burns
- Syncope
- Transient ischemic attack
- Vasovagal reactions
- Vasovagal episodes

- Pneumothorax
- Vasospasm

Possible adverse events associated with the renal denervation procedure include, but are not limited to:

- Acute renal injury (renal infarction, renal hematoma)
- Renal vascular injury (renal artery dissection, renal artery thrombosis, renal artery stenosis)
- Collateral tissue injury
- Malignant or accelerated hypertension
- Symptomatic hypotension
- Access site complications (arteriovenous fistula, access site thrombosis, embolisation, pseudo-aneurysm, hematoma, limb ischemia, femoral nerve injury, or seroma)
- Disseminated intravascular coagulation
- Infection (access site infection or systemic infection)
- Renal failure
- Decompensated heart failure
- Myocardial infarction
- Neurologic event (acute ischemic or hemorrhagic brain injury)
- Respiratory compromise
- · Pain, including back pain
- Death
- Drug reactions
- Contrast allergies etc

SJM CONFIDENTIAL AND PROPRIETARY

© 2013 – St. Jude Medical Cardiovascular Division: All rights reserved. No portion of this work may be reproduced in whole or in part without the express written permission of St. Jude Medical Cardiovascular Division.

Clinical Investigational Plan: RDN + AF

6.2 Steps that will be taken to control or mitigate the risks

Every possible effort will be taken to minimize the risks, including:

- Careful selection of experienced investigators for the clinical investigation
- Regular clinical investigation monitoring visits for each clinical investigation center
- Conduction of the clinical investigation in accordance with the Clinical Investigational Plan (CIP), all applicable laws and regulations (e.g. ISO14155:2011) and any conditions of approval imposed by the appropriate EC or applicable regulatory authorities where the clinical investigation is performed
- Performance of the cardiac ablation procedure in accordance with device IFUs.
- Preparation of the catheter and performance of the renal denervation procedure in accordance with the device IFUs.
- Catheter advancement under fluoroscopic imaging to minimize the risk of arterial damage.
- Training of Investigators both on the CIP and EnligHTN Renal Denervation procedure

6.3 Potential Benefits

There may not be any benefits from this research. For subjects randomized to the renal denervation arm of the study, possible benefits may include a decrease in blood pressure, which may also have beneficial effects on the heart such as a reduced chance of arrhythmia recurrence. Previous studies of renal denervation have reported varying results. One randomized trial using a different product and conducted in the United States, showed no benefit in blood pressure reduction.³² The RD+AF trial uses a different product and aims to study the impact of renal denervation on atrial fibrillation. Less than 20% of patients in previous studies had no significant reduction in blood pressure and the majority of patients in a small study had an improvement in the atrial fibrillation recurrence. Information gathered from this study will add to the understanding of the treatment options for patients with atrial fibrillation and high blood pressure. This knowledge may advance medical science and may, in turn, benefit other patients with atrial fibrillation and high blood pressure.

7 Statistical Analysis

7.1 Study design

This is a post market, prospective, multicenter, 2:1 randomized study of the EnligHTN™ Renal Denervation System in conjunction with atrial fibrillation ablation. Up to one hundred subjects with paroxysmal or persistent atrial fibrillation and uncontrolled hypertension will undergo atrial fibrillation ablation. Per the 2:1 randomization, a minimum of 50 or 2/3 of the total patient cohort will also undergo renal artery ablation. Subjects will be followed up to years (2) years post procedure.

To assess the feasibility of concomitant cardiac ablation for the treatment of atrial fibrillation and renal denervation ablation using the EnligHTN renal denervation system in achieving freedom

from atrial fibrillation in patients with hypertension. Freedom from atrial fibrillation will be assessed based on electrocardiographic data during nine months following the blanking period.

7.2 Sample size estimation

The sample size of approximately 100 patients is used considering the study purpose: to complete a preliminary evaluation on whether or not concomitant renal denervation with the EnligHTN™ Renal Denervation System and cardiac ablation will result in improved outcomes as compared to ablation alone in patients being treated for Atrial Fibrillation. Of these patients, a minimum of 50 patients (or 2/3 of the total patient cohort) will undergo both a cardiac ablation procedure and a concomitant renal denervation procedure.

No formal power analysis or hypothesis test will be performed. However the data collected will be analyzed and presented using the descriptive or appropriate summary statistics.

7.3 Analysis Population

All patients who have signed a Patient Informed Consent (PIC) will be considered enrolled in the study. However, the Primary Analysis population will only include those patients that have signed a PIC, have undergone a cardiac ablation procedure for the treatment of atrial fibrillation, and, if in the renal denervation arm of the study, had the EnligHTN™ Renal Denervation System enter his/her body.

It is anticipated that there may be subjects who have been enrolled in the study but are not included in the Primary Analysis population, such as:

- Subjects who are enrolled but do not meet baseline inclusion or exclusion criteria before the procedure; these are considered the screen failure population.
- Procedurally excluded populations will include subjects who have enrolled in the study and start the procedure, but do not undergo a cardiac ablation procedure for the treatment of atrial fibrillation or if in the renal denervation arm of the study and do not have the EnligHTN™ Renal Denervation System enter his/her body, due to their anatomy, circumstances related to the procedure, or physician judgment.

Subjects who withdraw from the investigation will not be replaced in any analysis population.

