3.1 Purpose

The purpose of this post market clinical investigation is to evaluate if concomitant renal denervation with the EnligHTN™ Renal Denervation System and cardiac ablation will result in improved outcomes as compared to ablation alone in patients with uncontrolled hypertension being treated for atrial fibrillation.

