4.3 Randomization Procedure

Using a 2:1 randomization scheme, each subject will be randomized to an atrial ablation procedure with concomitant renal denervation or an atrial ablation procedure alone.

Each subject will be randomized after the following is completed:

- Baseline evaluation
- Inclusion/Exclusion evaluation
- Subject signs study-specific consent form
- Cardiac ablation procedure for treatment of atrial fibrillation is complete.

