#### 2.2 Sample size estimation

The sample size of 75 patients is used considering the study purpose: to complete a preliminary evaluation on whether or not concomitant renal denervation with the EnligHTN™ Renal Denervation System and cardiac ablation will result in improved outcomes as compared to ablation alone in patients being treated for Atrial Fibrillation. Of these patients, a minimum of 50 patients (or 2/3 of the total patient cohort) will undergo both a cardiac ablation procedure and a concomitant renal denervation procedure.

No formal power analysis or hypothesis test will be performed. However the data collected will be analyzed and presented using the descriptive or appropriate summary statistics.

All patients who have signed a Patient Informed Consent (PIC) will be considered enrolled in the study.

However, the Primary Analysis population will only include those patients that have signed a PIC, have undergone a cardiac ablation procedure for the treatment of atrial fibrillation, and, if in the renal denervation arm of the study, had the EnligHTN™ Renal Denervation System enter his/her body.

It is anticipated that there may be subjects who have been enrolled in the study but are not included in the Primary Analysis population, such as:

- Subjects who are enrolled but do not meet baseline inclusion or exclusion criteria before the procedure; these are considered the screen failure population.
- Procedurally excluded populations will include subjects who have enrolled in the study and start the procedure, but do not undergo a cardiac ablation procedure for the treatment of atrial fibrillation or if in the renal denervation arm of the study and do not have the EnligHTN™ Renal Denervation System enter his/her body, due to their anatomy, circumstances related to the procedure, or physician judgment.

Subjects who withdraw from the investigation will not be replaced in any analysis population. All available data from these subjects will be included in summary statistics and analyses where applicable.

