#### 2.3 Data Analysis and Reporting

Data analysis will be performed across all subjects based on Primary Analysis population unless otherwise specified.

The data collected will be presented using the appropriate summary statistics. Continuous data will be summarized using descriptive statistics (mean, number of observations, standard deviation, minimum and/or maximum values) and categorical data will be summarized using frequencies and percentages.

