#### 2.4 Primary objective

The primary objective is to assess the feasibility of concomitant cardiac ablation for the treatment of atrial fibrillation and renal denervation ablation using the EnligHTN renal denervation system in achieving freedom from atrial fibrillation in patients with hypertension.

Project Code: SJM-CIP-0009 Project Name: RD+AF

The freedom from atrial fibrillation will be assessed based on electrocardiographic data during nine months following the blanking period including the one week recording coinciding with the 12 month follow-up visit (9 months following the 3 month blanking period). AF recurrence during the blanking period will not qualify as an endpoint event per protocol. Subjects may be re-treated with up to two repeat ablation procedures during the course of the study with a 3 month blanking period following the treatment. Assessment of the AF recurrence will be determined through evaluation of 12 lead ECG recordings, holter monitoring or event recorder results. AF Recurrence is defined as episodes lasting longer than 30 seconds in duration unless detected via 12-lead EKG. To count as a study-related recurrence, the AF episode must be documented on the AF Recurrence Evaluation CRF. For this study, AF also includes (documented >30 seconds) atrial flutter and atrial tachycardia.

No formal hypothesis testing will be performed. An overall percentage of subjects experiencing an event will be summarized for each randomization arm and is defined as:

Number of subjects with AF recurrence within 12 months post procedure Number of subjects with at least 12 months of follow – up or experienced AF recurrence \* 100

Subjects who exit the study prior to 12 month visit without AF recurrence will be excluded from the percentage to prevent under-estimation of the event rate. Kaplan-Meier analysis may be performed to provide freedom from atrial fibrillation rates at one year for each randomization arm using date of ablation procedure to date of first event.

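### The default analysis set can drop randomised patients from the renal-denervation arm only, and no all-randomised summary of AF recurrence is planned

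*Protocol*

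**What the plan says.** SAP 2.2 states that "the Primary Analysis population will only include those patients that have signed a PIC", have undergone cardiac ablation and, in the renal-denervation (RDN) arm, meet the device-entry condition "if in the renal denervation arm of the study, had the EnligHTN™ Renal Denervation System enter his/her body". Protocol 7.3 has the same three conditions. Both documents allow device entry to fail because of anatomy, procedural circumstances or physician judgment.

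SAP 2.3 makes this set the default: "Data analysis will be performed across all subjects based on Primary Analysis population unless otherwise specified". Protocol 7.4 agrees. SAP 2.4 then says: "An overall percentage of subjects experiencing an event will be summarized for each randomization arm". SAP 2.5.3 applies the same definition at 3, 6 and 24 months. Neither section names another set.

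Protocol 4.3 lists what must precede randomisation. The last item is "Cardiac ablation procedure for treatment of atrial fibrillation is complete".

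Two other populations appear. An As Treated analysis is optional (protocol 7.4.3, SAP 2.6). SAP 2.5.2 divides by all subjects randomised to RDN, but only for renal vascular safety.

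The primary objective is feasibility, and no hypothesis test is planned. The purpose in protocol 3.1 is nevertheless comparative: whether adding RDN "will result in improved outcomes as compared to ablation alone".

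**The concern.** Randomisation makes the arms comparable in expectation only if patients are analysed in the arm they were assigned to. A condition applied after assignment, in one arm only and partly at the operator's discretion, can make the kept RDN patients differ in prognosis from the controls. A descriptive comparison is exposed to this just as a test is. SAP 2.3 lists frequencies and percentages for categorical data, with no interval, so readers would see two arm percentages with nothing to show that one arm had been filtered. At stake is the RDN-versus-control reading of AF recurrence, not the description of the procedure.

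**Working it through.** **The plan's own figure.** There is no power calculation to reproduce. The stated minimum of 50 RDN patients is 2/3 of the SAP total: 75 × 2/3 = 50, leaving 25 controls. With the protocol's total of about 100, 100 × 2/3 = 66.7, so 50 is then only a floor. The point here does not depend on which total is right.

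**Which conditions can fail after randomisation.**

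1. Signed consent: required before randomisation (4.3), so it cannot fail afterwards.
2. Cardiac ablation: completed before randomisation (4.3). Screen failures are likewise defined as failing the criteria before the procedure.
3. Device entry: can fail, in the RDN arm only.

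The population rule can thus remove some randomised RDN patients and no controls. If a site randomised before ablation, contrary to 4.3, controls could be lost too.

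**How large the bias could be.** The documents give no exclusion share and no outcome for excluded patients, so these are assumptions: 50% AF-free in both randomised arms, no true effect, a share q of the RDN arm excluded, and an AF-free rate a among those excluded.

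Bias in the RDN AF-free rate = q × (0.50 − a) / (1 − q)

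If 50 treated patients are retained (protocol 3.11) and k are excluded, q/(1 − q) = k/50.

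| Excluded from RDN arm | a = 30% or 70% | a = 0% or 100% |
|---|---|---|
| 5% | 0.05 × 0.20 / 0.95 = ±1.05 points | ±2.63 |
| 10% | 0.10 × 0.20 / 0.90 = ±2.22 | ±5.56 |
| 1 of 51 | 1/50 × 0.20 = ±0.4 | ±1.0 |
| 3 of 53 | ±1.2 | ±3.0 |
| 5 of 55 | ±2.0 | ±5.0 |

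The bias favours RDN if excluded patients do worse than average, and the reverse if they do better.

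**Against sampling error.** Half-width of the 95% interval for the difference, at 50% in each arm = 1.96 × √(0.25/n₁ + 0.25/n₂):

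- 67 v 33: 20.8 points
- 55 v 27: 23.0 points
- 50 v 25: 24.0 points

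**Why a new population label is not enough.** SAP 2.4 also says: "Subjects who exit the study prior to 12 month visit without AF recurrence will be excluded from the percentage". An RDN subject terminated at the procedure would leave the percentage under this rule whatever the set is called. Kaplan-Meier would not help either. Its clock starts at ablation and no event counts in the first three months, so a subject censored on the procedure day is in no risk set at an event time. Both estimators would return the device-entered result.

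The early-exit rule is otherwise a separate issue that affects both arms. Assume exits are uniform over months 3 to 12 and unrelated to AF, the recurrence hazard is constant after month 3, and true recurrence at month 12 is 50%. At 5%, 10% and 20% exits, the SAP percentage becomes 50.7%, 51.5% and 53.3% if recurrence is detected continuously, or 50.4%, 50.8% and 51.7% if it is detected only at the month 6 and 12 recordings.

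**The case against.** The strongest reply is that this is a feasibility study with no test and no decision rule tied to this set, and that the filter is light. A patient whom the device entered stays in, even if only one side was treated (protocol 7.4.3, SAP 2.6). Any plausible bias is about a tenth of the half-width or less. This largely stands. It limits the seriousness of the point and justifies keeping the device-entered set. It does not answer the comparative purpose, for which an all-randomised summary is missing. As Treated does not supply one, since it is optional and not all-randomised.

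Pre-randomisation screening of anatomy is only partly reassuring. Protocol 3.7.2 excludes small or stenosed renal arteries, and 4.1.10 places imaging before enrolment. However, Table 1 marks baseline renal imaging as applying to the RDN group only, while Table 2 does not. On the Table 1 reading, unsuitable anatomy could first be found after assignment.

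Two stronger readings are tempting:

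- **That the rule inflates the benefit of RDN.** In the small study cited in the protocol background, recurrence was 4/13 (30.8%) with RDN and 10/14 (71.4%) without. If 5 of 50 RDN patients were dropped and recurred at the control rate, all-randomised RDN recurrence would be higher by 5/50 × (71.4 − 30.8) = 4.1 points. Nothing in the documents says that excluded patients would fare this way.
- **That protocol 3.8 contradicts 4.11.** Section 3.8 sends procedural exclusions to the Termination CRF, and 4.11 follows each subject for two years. But 4.11 also allows earlier exit, and its termination reasons include completing the study. This is an ambiguity, not a shown contradiction.

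**Conclusion.** The point holds in this limited form. Under protocol 4.3, the default set can lose randomised patients from the RDN arm only, and no all-randomised summary of AF recurrence is specified. The size rests on assumed values: about ±1 to ±2 points at 5% to 10% excluded, with extremes of ±2.6 to ±5.6 and direction unknown, against sampling error of 21 to 24 points. A reader should not infer that the feasibility description is invalid or that the result is known to lean towards RDN. The case for change is that the exclusion is avoidable at little cost and that the stated purpose is a comparison.

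**What to change.** 1. In protocol 7.3 and SAP 2.2 to 2.4, report AF recurrence for all randomised subjects by assigned arm as the basis for the between-arm comparison. Keep the device-entered set as supportive.
2. Apply the same estimators to both sets: the SAP 2.4 percentage and the Kaplan-Meier estimate the SAP already allows ("Kaplan-Meier analysis may be performed to provide freedom from atrial fibrillation rates at one year for each randomization arm"). Changing population and estimator together would hide the effect of the exclusion.
3. As part of the main fix, reconcile 3.8 with 4.11, so that it is clear whether RDN-arm subjects without device entry remain in scheduled AF follow-up. If they leave at the procedure, step 1 changes nothing.
4. Tabulate post-randomisation exclusions by arm and reason.
5. Reconcile Tables 1 and 2 on who has baseline renal imaging.

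The cost is revised wording, one further summary and one table. If the few subjects without device entry would otherwise exit, it also includes their scheduled visits and recordings. No extra patients are needed. The RDN estimate may move slightly in either direction.
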